9.3.2 Statistical model, hypothesis, and method of analysis

The analysis will be mainly based on summary statistics, no inferential statistical analysis is planned. The graphical summaries on PK concentration will also be provided.

9.3.3 Handling of intercurrent events of primary estimand (if applicable)

All PK data will be presented as recorded in the descriptive statistics. For participants who discontinue from study or death where PK information is not available, the impact of this on the interpretation of the results will be considered. Additional summaries as needed to support this interpretation may be presented. It is not intended to impute missing data after discontinuation.

9.3.4 Handling of missing values not related to intercurrent event

Missing primary endpoint values due to protocol deviations or other issues related to a pandemic are not anticipated as measures have been put in place, where possible, to allow for the protocol assessments to be conducted. In case missing values do occur for such reasons, only data available will be used.

9.3.5 Sensitivity analyses

No sensitivity analyses are planned.

9.3.6 Supplementary analysis

No subgroup analyses or other supplementary analyses are planned.

9.4 Secondary endpoint(s)/estimand(s) analysis

The analysis for secondary endpoints will be based on descriptive statistics by treatment group.

9.4.1 Efficacy and/or pharmacodynamic endpoint(s)

The secondary endpoint is all safety. There is no efficacy analysis in secondary endpoint.

9.4.2 Safety endpoints

For all safety analyses, the safety set will be used. All listings and tables will be presented by treatment group.

Safety summaries (tables, figures) include only data from the on-treatment period with the exception of baseline data which will also be summarized where appropriate (e.g. change from baseline summaries).

Adverse events

All information obtained on adverse events will be displayed by treatment group and participant.

The number (and percentage) of participants with treatment emergent adverse events (events started after the first dose of study medication or events present prior to start of participant and investigator-blind treatment but increased in severity based on preferred term) will be summarized in the following ways:

- by treatment, primary system organ class and preferred term.
- by treatment, primary system organ class, preferred term and maximum severity.
- by treatment, Standardized MedDRA Query (SMQ) and preferred term.

Separate summaries will be provided for study medication related adverse events, death, serious adverse events, other significant adverse events leading to discontinuation.

The number (and proportion) of participants with adverse events of special interest/related to identified and potential risks will be summarized by treatment.

A participant with multiple adverse events within a primary system organ class is only counted once towards the total of the primary system organ class.

The following adverse events will be counted during 90-day study period:

- These events are those with an onset after the start of the treatment period, or which were present prior to the start of the treatment period but increased in severity, changed from being not suspected to being suspected of study treatment relationship, or developed into SAEs after the start of the treatment period.

Vital signs

Summary statistics will be provided for all vital signs data by treatment and visit/time. Where ranges are available, abnormalities (and relevant orthostatic changes) will be listed by treatment group, participant, and visit/time. If appropriate, summary statistics of the occurrence of abnormalities may be provided by treatment.

Clinical laboratory evaluations

Summary statistics for all laboratory data will be provided by treatment and visit/time. Shift tables using the low/normal/high/ (low and high) classification may be used, as appropriate, to compare baseline to the worst on-treatment value. Where normal ranges are available, abnormalities in laboratory data will be listed by treatment group, participant, and visit/time.

Graphical displays of selected safety parameters (e.g. hematological parameters, thyroid and reproductive hormone levels) over time will be provided by treatment group.

[figure not shown]
Immunogenicity

All immunogenicity results will be listed by cohort, treatment group, subject and visit/time. The listing will contain ADA status (negative or positive) and for ADA-positive samples a titer and ADA neutralization potential of TIN816 and/or endogenous CD39. Subjects with one or more treatment emergent ADAs are counted as ADA-positive subjects and they will be summarized by treatment arm to derive an ADA incidence. Incidences for neutralizing ADAs will be assessed as well, if appropriate. Visualizations overlaying ADA status including characterizations, along with PK concentration and potentially efficacy read-outs, will be presented.

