2.2 Background

During sepsis, a dysregulated host response to infection leads to a life-threatening multi-organ dysfunction. Sepsis is a leading cause of death and a major public health problem that affects millions of patients worldwide every year (Fleischmann et al., 2016, Rudd et al., 2020). In the United States (US) alone, an estimated 1.7 million adults present to hospital each year with sepsis with up to 270,000 deaths resulting (Rhee et al., 2017). An aging population and an increase in underlying comorbidities have led to continuous growth in the incidence of sepsis (Mayr et al., 2014).

Approximately 90% of sepsis is caused by bacterial infection and 40-60% of septic patients experience sepsis-associated acute kidney injury (SA-AKI) (Liu et al., 2020, Yu et al., 2021). Acute kidney injury (AKI) refers to an abrupt decrease in kidney function, resulting in the retention of urea and other nitrogenous waste products and in the dysregulation of extracellular volume and electrolytes. It is estimated that ~813,000 patients suffer from SA-AKI in the US, ~793,000 in urban China, ~232,000 in Japan and ~79,000 in Germany (Fleischmann-Struzek et al., 2018, Peters et al., 2018, Tian et al., 2019, Imaeda et al., 2021).

Development of AKI in patients with sepsis is associated with significantly increased mortality rate of up to 65%, and survivors are at significantly increased risk of developing chronic kidney disease (CKD) and kidney failure, resulting in a significant health and financial burden for both patient and society (Peerapornratana et al., 2019, Chua et al., 2020, Liu et al., 2020).

SA-AKI is a multifactorial syndrome with inflammatory, nephrotoxic, and ischemic insults occurring simultaneously with other pathophysiological responses rapidly leading to kidney impairment. Over the last 30 years, there were a considerable number of potential drug targets and the development of new therapies to treat sepsis and/or AKI. Attempts were primarily focusing on improving hemodynamics, reducing oxidative stress, and blocking hyper-inflammatory response; however, all of which have failed in clinical trials (Cohen et al., 2015, Kellum et al., 2021). As a result, there are currently no specific pharmacological agents available for the treatment of SA-AKI. Management of patients with SA-AKI relies mainly on targeted antibiotics and supportive treatment including fluid resuscitation, vasoactive agents and renal replacement therapy (RRT).

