4.3 Justification for dose

The in vitro potency for TIN816 in whole blood (WB) assays (LPS/ATP induced IL-1 β release and ADP-induced platelet aggregation) was demonstrated to be comparable for rat, minipig and human. The similarity in pharmacology across species allowed to predict and explore an exposure range expected to be safe in light of animal safety and pharmacology data and reaching expected therapeutic doses. These PD whole blood assays revealed in-vitro IC90s of approximately 1.66 to 2.66 μ g/mL for human.

In a FIH study in healthy volunteers, a starting dose of 0.1 mg/kg and subsequent doses of 0.3, 1.0 and 2.0 mg/kg were selected in accordance

with [CHMP \(2017\)](#) and [CDER \(2005\)](#) guidelines. The administration of 0.1, 0.3, 1.0 and 2.0 mg/kg of TIN816 or placebo as a single IV infusion was well tolerated and did not reveal any safety signals related to the investigational medicinal product (IMP). The effect of TIN816 on purinergic signaling was assessed in two ex-vivo PD assays in whole blood by studying inhibition of LPS/ATP induced IL-1 β release and inhibition of ADP induced platelet aggregation. Ex-vivo, an IC90 of 0.25 μ g/mL was derived for inhibition of ADP-induced platelet aggregation and an IC90 of 7.8 μ g/mL for inhibition of LPS/ATP-induced IL-1 β release. In FIH, exposure was determined systemically and in skin interstitial fluid. Results indicate that TIN816 may attenuate purinergic signaling systemically for roughly three weeks at a dose of 2 mg/kg. This conclusion depends; however, on the PD assay considered (LPS/ATP induced IL-1 β release or ADP-induced platelet aggregation, assessed in-vitro or ex-vivo), on the relevance of the determined inhibiting TIN816 concentrations (e.g. IC50s, IC90s) for the clinical situation and on the required exposure in the relevant tissues.

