5.2 Exclusion criteria

Participants meeting any of the following criteria at screening assessment, unless otherwise specified at randomization (Day 1) , are not eligible for inclusion in this study.

1. Not expected to survive for 24 hours.
2. Not expected to survive for 30 days due to medical conditions other than SA-AKI.
3. History of CKD with a documented estimated GFR <45 ml/min prior to development of AKI.
4. Receiving RRT or a decision has been made to initiate RRT within 24 hours of admission.
5. Weight is less than 40 kg or more than 125 kg .
6. Has life support limitations (eg, do not resuscitate, do not dialyze, do not intubate).
7. AKI diagnosis according to the AKI inclusion criteria for a period longer than 48 hours prior to study drug administration.
8. Presence of AKI for a period longer than 48 hours prior to study drug administration as suggested by clinical manifestations, e.g., prolonged oliguria or severe renal dysfunction (eg, serum creatinine > 4 mg/dL) on admission without a history of CKD.
9. Evidence of recovery from AKI based on the investigator's clinical judgement prior to randomization.
10. AKI is most likely attributable to causes other than sepsis such as nephrotoxic drugs (Non-steroidal anti-inflammatory drugs (NSAIDs), contrast, aminoglycosides), other medical conditions (e.g. heart failure, liver failure, acute abdominal aortic aneurysm, dissection, renal artery stenosis) or urinary obstruction.
11. Documented (biopsy proven) or suspected history of acute or sub-acute kidney diseases such as rapidly progressive glomerular nephritis (RPGN) and acute interstitial nephritis (AIN).
12. Patients who are post-nephrectomy.
13. Patients who are on dual antiplatelet therapy.

14. Patients who are thrombocytopenic at screening (Platelet count <100,000 microliter) or other high risk for bleeding in the opinion of the investigator.
15. Immunosuppressed patients:
 - History of immunodeficiency diseases or known HIV test positive.
 - Is receiving immunosuppressant treatment or is on chronic high doses (high-dose therapy exceeding 2 weeks of treatment) of steroids equivalent to prednisone/prednisolone 0.5 mg/kg/day, including solid organ transplant patients. Patients with septic shock treated with hydrocortisone (e.g., 3 × 100 mg) can be included.

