9.1 Analysis sets

The Randomized Analysis Set (RAS) consists of all randomized participants. This analysis set will not be used for any analyses and is solely intended for providing complete information on how participants were randomized.

The PK analysis set will include all participants who survive Day 7 with at least one available valid (i.e., not flagged for exclusion) PK concentration measurement, who received complete study drug regardless of infusion duration.

The PD analysis set will include all participants with available PD data. Participants will be analyzed according to actual study treatment received.

The full analysis set (FAS) comprises all participants to whom study treatment has been assigned by randomization. According to the intent to treat principle, participants will be analyzed according to the treatment they have been assigned to during the randomization procedure. Mis-randomized participants, that is, participants who were randomized incorrectly

and did not receive any study drug will be excluded from this set. This will be the analysis set used for all efficacy analyses.

The safety set (SAF) includes all participants who received one dose of study treatment. Participants will be analyzed according to the study treatment received, where treatment received is defined as the participant took at least one dose of that study treatment regardless treatment group randomized to. This will be the analysis set used for safety analysis except for PK/PD analysis.

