2.6.1 Secondary endpoints/secondary estimands

For all safety analyses, the safety set will be used. All summaries where appropriate (e.g. change from baseline summaries), listings and tables will be presented by treatment group.

Adverse events

All information obtained on adverse events will be displayed by treatment group and participant.

The number (and percentage) of participants with treatment emergent adverse events (events started after the first dose of study medication or events present prior to start of participant and investigator-blind treatment but increased in severity based on preferred term) will be summarized in the following ways:

- by treatment, primary system organ class and preferred term.
- by treatment, primary system organ class, preferred term and maximum severity.

Separate summaries will be provided for study medication related adverse events, death, serious adverse events, other significant adverse events leading to discontinuation.

The number (and proportion) of participants with following adverse events of special interest/related to potential risks will be summarized by treatment:

- bleeding
- perivascular/vascular mineralization
- infusion reaction and hypersensitivity
- anti-drug antibody mediated reactions (immunogenicity).

A participant with multiple adverse events within a primary system organ class is only counted once towards the total of the primary system organ class.

The following adverse events will be counted during 90-day study period:

- These events are those with an onset after the start of the treatment period, or which were present prior to the start of the treatment period but increased in severity, changed from being not suspected to being suspected of study treatment relationship, or developed into SAEs after the start of the treatment period.

Vital signs

Summary statistics will be provided for all vital signs data by treatment and visit/time. Where ranges are available, abnormalities (and relevant orthostatic changes) will be listed by treatment group, participant, and visit/time. If appropriate, summary statistics of the occurrence of abnormalities may be provided by treatment.

Graph of mean arterial pressure (MAP) over time will be provided by treatment. Of note MAP is defined as diastolic blood pressure + 1/3*pulse pressure, where pulse pressure =systolic blood pressure – diastolic blood pressure).

Clinical laboratory evaluations

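### Adverse events are compared only as a crude 90-day percentage, which understates non-fatal and special-interest events in an arm with more early deaths and dilutes an early effect

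*Protocol*

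**What the plan says.** The secondary objective is safety and tolerability of TIN816 versus placebo (Protocol Table 3-1). The planned AE measure, the same in Protocol 9.4.2 and SAP 2.6.1, is "The number (and percentage) of participants with treatment emergent adverse events". Events of special interest are likewise given as number and proportion by treatment. The counting rule in both documents is "The following adverse events will be counted during 90-day study period". The denominator comes from Protocol 9.1: "The safety set (SAF) includes all participants who received one dose of study treatment".

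Protocol 9.4.2 also contains a restriction that does not fit the 90-day rule: "Safety summaries (tables, figures) include only data from the on-treatment period with the exception of baseline data". No such period is defined for a single 2-hour infusion. SAP 2.6.1 omits the sentence. However, SAP 2.1 refers back to Protocol Section 9, and SAP Section 4 does not list the omission as a change.

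SAP 2.4.1 computes a duration of study that stops at death, but no AE table in the readable text uses it. Neither document gives an event rate, participant-days, numbers at risk or a split by time of onset.

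On mortality, Protocol 2.2 says: "Development of AKI in patients with sepsis is associated with significantly increased mortality rate of up to 65" per cent. On duration of action, Protocol 4.3 says: "Results indicate that TIN816 may attenuate purinergic signaling systemically for roughly three weeks at a dose of 2 mg/kg".

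**The concern.** A participant who dies on Day 5 stays in the denominator for 90 days but can have no further event. The crude percentage therefore depends on how long each arm survives as well as on how often events occur. For non-fatal events, an arm with more early deaths has less time in which to show them.

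The second problem is timing. If the drug acts for about 21 days, the remaining 69 days add background events to both arms and pull their ratio towards 1. Bleeding, the first-listed event of special interest, is tied to platelet inhibition and is where an early excess would be looked for. These tables will inform further development, so an avoidable distortion in them matters even without a formal test.

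**Working it through.** The plan states no expected AE percentage, so there is no AE figure to reproduce. Its only design calculation is for PK precision. With n = 15 and GCV 0.25, exp(t(0.975, 14) × √ln(1.0625) / √15) = 1.146, which agrees with the stated 15%. The arm sizes are 20 × 3/4 = 15 and 20 × 1/4 = 5. All hazards, mortality splits and death times below are assumptions.

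**1. Unequal early mortality, identical AE hazard.** A share p of the arm dies at Day 10 and the hazard of a first non-fatal event is h per day. The crude 90-day proportion is p(1 − e^(−10h)) + (1 − p)(1 − e^(−90h)).

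| h per day | p = 20% | p = 60% |
|---|---|---|
| 0.005 | 30.0% | 17.4% |
| 0.01 | 49.4% | 29.4% |
| 0.02 | 70.4% | 44.3% |

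For h = 0.01 and p = 0.6: 0.6 × 0.0952 + 0.4 × 0.5934 = 0.294. A milder contrast at h = 0.01, 40% against 20% dying, gives 39.4% against 49.4%.

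**2. Deaths spread over the first 14 days.** Let λ = −ln(0.6)/90 (a 40% event risk by Day 90 if nobody died), μ = −ln(1 − M)/14 and k = λ + μ. The crude proportion is (λ/k)(1 − e^(−14k)) + e^(−14k)(1 − e^(−76λ)).
- Mortality M of 0, 20, 40 and 65% gives 40.0, 32.7, 25.4 and 16.1%.
- At 65% versus 40% mortality, a true hazard ratio of 1 shows as 16.1/25.4 = 0.63, and a true ratio of 2 shows as 1.04.
- With 40% mortality in both arms, ratios of 1 and 2 show as 1.00 and 1.62.

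**3. Counting fatal events.** If each death is itself an event, the step 1 proportion becomes p + (1 − p)(1 − e^(−90h)). At h = 0.01 this is 84% for p = 60% and 67% for p = 20%, so the arm with more deaths looks worse.

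**4. Dilution.** Use the same λ, doubled for 21 days, with no deaths.
- Day 21: (1 − e^(−42λ))/(1 − e^(−21λ)) = 21.2%/11.2% = 1.89.
- Day 90: (1 − e^(−111λ))/(1 − e^(−90λ)) = 46.7%/40.0% = 1.17.
- With a background 90-day risk of 20%, the ratio falls from 1.95 to 1.20; with 80%, from 1.69 to 1.08.

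**5. Chance imbalance in follow-up.** Simulated trials of 15 versus 5 had no mortality effect and exponential death times with mean 15 days. Mean follow-up differed at least 1.25-fold in about 42%, 54% and 65% of trials at 90-day mortality of 30%, 45% and 65%. One placebo death on Day 3 leaves 3 + 4 × 90 = 363 of 450 days, a loss of 19%.

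**6. Would one pooled 90-day rate suffice?** Take 3% per day to Day 10 and 0.3% afterwards, identical in both arms, with the deaths of step 1.
- By Day 10: events 1 − e^(−0.3) = 0.2592 over 0.2592/0.03 = 8.64 days at risk.
- Day 10 to 90, per survivor fraction: events 0.7408(1 − e^(−0.24)) = 0.1581 over 0.1581/0.003 = 52.7 days.
- Pooled rate at p = 60%: (0.2592 + 0.4 × 0.1581)/(8.64 + 0.4 × 52.7) = 1.08 per 100 days. At p = 20% it is 0.76. The ratio is a spurious 1.43.
- Cut at Day 21: the first 11 days after Day 10 contribute 0.0240 events over 8.02 days. The early-window rates are 2.27 and 1.85 (ratio 1.23), and the later window gives 0.30 in both arms.

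Windows therefore reduce this distortion but do not remove it.

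**The case against.** - **Deaths are not hidden.** Fatal is the first seriousness criterion in Protocol 8.6.2, and 8.6.5 exempts no disease-related events. Deaths and SAEs have separate summaries, fatal TEAEs are tabulated, all deaths are listed, and AEs are displayed by participant. With about 20 participants a large death imbalance would be the main result. This stands, and it limits the point to non-fatal and special-interest events. It does not supply an arm-level denominator for those events.
- **Mortality here is uncertain.** The 65% is an upper background figure with no time horizon. Eligibility also excludes those "Not expected to survive for 30 days due to medical conditions other than SA-AKI" and those not expected to survive 24 hours. This stands: the scenarios show direction and possible size and are not forecasts.
- **Noise is larger.** At a 40% event rate the standard error of a 15-versus-5 difference is √(0.24 × (1/15 + 1/5)) = 25 points, above the 20-point contrast at h = 0.01 in step 1. Exact 95% intervals are 5% to 85% for 2/5 and 16% to 68% for 6/15. The analysis is descriptive, and the chance imbalance in step 5 is extra variance rather than bias. This stands and lowers the priority. Still, the distortion is avoidable at little cost.
- **Day 21 is not the only defensible cut.** The three-week figure depends on the assay, and Protocol 6.7 gives at least 38 days for detectability. Hypersensitivity may be delayed by several weeks, minipig mineralization followed at least 35 days of low pyrophosphate, and antibodies are sampled to Day 90. This stands, so the later window must be kept.

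**Conclusion.** The point holds for non-fatal AEs and special-interest events. A crude 90-day percentage of all dosed participants understates them in an arm with more early deaths, and it dilutes an effect limited to the early weeks. Under the assumed scenarios the first effect reaches 20 to 26 points at 60% versus 20% early mortality for hazards of 1% to 2% per day, and it vanishes when mortality is equal. The second reduces a ratio of 1.89 to 1.17 at a 40% background risk. The actual size in this trial cannot be known from the documents.

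A reader might infer that the arm with more early deaths would look safer overall. The documents do not support that: fatal events count as AEs and SAEs and deaths are reported separately, so those totals move the other way (84% versus 67% in step 3). Nor do they support treating 65% as the expected mortality of this trial.

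Separately, Protocol 9.4.2 contradicts itself on the safety window, and the SAP settles it only by leaving a sentence out. The point is a low-cost improvement to the secondary analysis and does not affect the primary PK objective.

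**What to change.** In Protocol 9.4.2 and SAP 2.6.1:

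1. Keep the crude 90-day table. For non-fatal TEAEs and for each special-interest event, add a table by onset window. Take the cut from the documents' own figures (about Day 21 for activity, or Day 38 for detectability), fix it in advance, and keep the later window to Day 90.
2. For each window and arm, give the number alive and in follow-up at its start, participant-days at risk, and first events per 100 participant-days calculated within the window. Do not use one rate pooled over 90 days. State whether a participant with an event in the first window can count again in the second.
3. In the by-visit laboratory and vital-sign tables, show how many in each arm died before that visit.
4. Define or delete the on-treatment period in Protocol 9.4.2 so that it agrees with the 90-day counting rule, and record the change in SAP Section 4.

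The cost is wording and one or two extra tables from dates already collected. The rate assumes a roughly constant hazard within each window, and step 6 shows that some distortion remains if it is not.
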